### **9.7 Clinical Laboratory Abnormalities and Other Abnormal Assessments as AEs or SAEs**

Laboratory abnormalities are usually not recorded as AEs or SAEs. Clinical laboratory abnormalities that require medical or surgical intervention or lead to study drug interruption or discontinuation must be recorded as an AE or SAE, if applicable. The modified DAIDS Table for Grading the Severity of Adult and Pediatric AEs ([Appendix 1](#)) will be used to assess the severity of clinical laboratory abnormalities. In addition, clinical laboratory or other abnormal assessments (eg, ECG and vital signs) that are associated with signs and/or symptoms must be recorded as an AE or SAE if they meet the definition of an AE or SAE described in [Sections 9.1](#) and [9.6](#). If the clinical laboratory abnormality or abnormal assessment is part of a syndrome or diagnosis, record the syndrome or diagnosis (eg, anemia), not the clinical laboratory result (ie, decreased hemoglobin).

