#### **3.6.3. Definition of Study Phase and End of Study**

The analyses will include all the data collected in this study based on three phases defined as follows.

- **On-Treatment Phase:** when a subject is undergoing treatment with AB-729, VBR, or both per treatment group (ie, from first dose of either study drug through the last dose of VBR +1 day or last dose of AB-729 +56 days, whichever is later)
- **Off-Treatment Phase:** after a subject has discontinued AB-729, VBR, or both per treatment group, and prior to NrtI restart if applicable (ie, after the last dose of VBR +1 day or last dose of AB-729 +56 days, whichever is later, until the end of study or before the first dose of NrtI if it was restarted)
- **NrtI-Restart Phase:** after a subject has restarted NrtI, following the Off-Treatment Phase (ie, from the first dose of restarted NrtI through the end of study)

End of study is defined as when the last subject completes the last follow-up or is considered “lost to follow-up”, whichever is later.

Subjects may prematurely discontinue study drug earlier prior to the Week 48 visit. The end dates of the On-Treatment Phase may vary for individual subjects based on their last dose dates as defined in [Section 3.6.3](#).

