#### **7.1.5. Treatment-Emergent Adverse Events**

##### **7.1.5.1. Definition of Treatment-Emergent Adverse Events**

Treatment-emergent adverse events (TEAEs) are defined as any AEs with an onset date/time equal to or after the study drug start date/time through end of study .

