#### **7.1.6. Summaries of Adverse Events and Deaths**

Treatment-emergent AEs will be summarized based on the Safety Analysis Set. Tables will be created per study phase (i.e. On-Treatment Phase, Off-Treatment Phase, and NrtI-Restart Phase).

A brief, high-level summary of the number and percentage of subjects who experienced at least 1 TEAE in the categories described below will be provided by treatment group. The brief summary will also include treatment-related TEAEs, treatment-related TE SAEs, and TEAEs leading to premature study discontinuation. All deaths observed in the study will also be included in this summary. In addition, a table for each category showing the number and percentage of subjects will be provided by PT and treatment group in descending order of total frequency:

- TEAEs
- TEAEs by severity grade
- TEAEs related to AB-729
- TEAEs related to VBR
- TE SAEs
- TE SAEs related to AB-729
- TE SAEs related to VBR
- TEAEs leading to premature study drug AB-729 discontinuation
- TEAEs leading to premature study drug VBR discontinuation
- TEAEs leading to study discontinuation
- TEAEs leading to death (ie, outcome of death)

- COVID-19 specific TEAEs
- COVID-19 specific TE SAEs

Multiple events will be counted only once per subject in each summary. For summary by severity grade, the most severe grade will be used for those AEs that occurred more than once in an individual subject during the study.

A data listing containing all AEs will be provided.

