#### **7.2.1.2. Summaries of Laboratory Abnormalities**

A summary (number and percentage of subjects) for treatment-emergent laboratory abnormalities will be provided by lab test and treatment group; subjects will be categorized according to the most severe postbaseline abnormality grade for a given laboratory test.

Treatment-emergent lab abnormalities will be summarized based on the Safety Analysis Set. Tables will be created per study phase (i.e. On-Treatment Phase, Off-Treatment Phase, and NrtI-Restart Phase).

For all summaries of laboratory abnormalities, the denominator is the number of subjects with nonmissing postbaseline values in each phase.

The maximum post-baseline grade in each phase will be tabulated for each laboratory test, and percentages will be based on the number of subjects with a post-baseline evaluation of the specific laboratory test. The laboratory abnormalities during the follow-up period will also be summarized.

A by-subject listing of graded laboratory abnormalities will be provided by subject ID number and visit in chronological order. This listing will include all test results that were collected throughout the study for the lab test of interest, with all applicable severity grades displayed.

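### TEAE tables are produced by study phase, but the severity rule takes the worst grade over the whole study, so a grade reached in one phase can appear in another phase's table

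*Combined protocol and SAP*

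**What the plan says.** SAP 7.1.6 sets the layout of the AE tables: "Tables will be created per study phase (i.e. On-Treatment Phase, Off-Treatment Phase, and NrtI-Restart Phase"). Its counting rule is per table: "Multiple events will be counted only once per subject in each summary". The rule for the table by severity grade follows directly and has a different scope: "the most severe grade will be used for those AEs that occurred more than once in an individual subject during the study".

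Three other sections determine what that scope takes in:

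- SAP 7.1.5.1 defines TEAEs as "any AEs with an onset date/time equal to or after the study drug start date/time through end of study". Events after treatment are therefore TEAEs and can enter the tables.
- SAP 3.6.3 defines the On-Treatment Phase as running "from first dose of either study drug through the last dose of VBR +1 day or last dose of AB-729 +56 days, whichever is later". The Off-Treatment and NrtI-Restart Phases follow it.
- SAP 7.2.1.2, the parallel section for laboratory grades, states the phase limit: "The maximum post-baseline grade in each phase will be tabulated for each laboratory test".

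SAP 7.1.6 does not say how an AE is assigned to a phase. SAP 3.6.3 gives the phase boundaries but does not say that onset date decides.

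**The concern.** Separate phase tables let a reader tell events under VBR and AB-729 from events after those drugs end, including events after NrtI is withdrawn. A severity grade taken over the whole study undoes that separation for any preferred term that recurs across phases. The On-Treatment table can show a grade that the subject reached only later, and the Off-Treatment table a grade that the subject reached only earlier.

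Safety and tolerability is the primary objective. Protocol 10.4.5 names TEAE severity as part of the safety analysis, and protocol 10.4.5.1 requires a summary of TEAEs by grade. Two programmers following the same sentence could produce different versions of that table.

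**Working it through.** The plan gives no figure to reproduce: the sample size is not based on statistical considerations, and the point is a tabulation rule. The check applies the rule under each reading to one invented subject and then gives the weight of one subject.

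**Step 1. Scope of each rule.**

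| Item | Section | Scope as written |
|---|---|---|
| AE tables | SAP 7.1.6 | each phase |
| Counting of repeat events | SAP 7.1.6 | each summary |
| Grade of a recurring AE | SAP 7.1.6 | the study |
| TEAE window | SAP 7.1.5.1 | first dose to end of study |
| Maximum laboratory grade | SAP 7.2.1.2 | each phase |
| Abnormal direct bilirubin | SAP 7.2.2 | the phase |

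The severity rule for recurring AEs is the only grading rule here that names the study as its scope while feeding tables built by phase.

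**Step 2. One subject, two readings.** Take a subject with one preferred term recorded twice: Grade 1 on treatment and Grade 3 off treatment.

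| Phase table | Recorded grade | Maximum over the study | Maximum within the phase |
|---|---|---|---|
| On-Treatment | 1 | max(1, 3) = 3 | 1 |
| Off-Treatment | 3 | max(1, 3) = 3 | 3 |

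If the order is reversed (Grade 3 on treatment, Grade 1 off), the study-wide maximum again gives 3 in both tables, and the Off-Treatment table is the one inflated. The effect can run either way.

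**Step 3. Weight of one subject.** Planned group sizes are 30, 15 and 15 (protocol Table 7, SAP Table 1-2). Taking these as denominators, one such subject moves this share of the group to the higher grade in the row for that preferred term:

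- Group 1: 1/30 = 3.3 percentage points.
- Group 2 or 3: 1/15 = 6.7 percentage points.

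**Step 4. What does not move.** Whether a subject had a given TEAE in a phase does not depend on its grade. Counts of TEAEs, SAEs, related TEAEs, discontinuations and deaths are therefore the same under both readings. Laboratory grades follow SAP 7.2.1.2 and stay within the phase.

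**The case against.** The strongest reply is that the context already supplies the phase limit. The tables are per phase, repeat events are counted once in each summary, and the severity sentence concerns one of those summaries. A programmer who filters to on-treatment events first and then takes the maximum carries nothing across phases. Nothing in the SAP says that an off-treatment grade is to be brought back. SAP 7.2.1.2 also contains a sentence on the most severe post-baseline grade without a phase limit, before a later sentence supplies one, so the study-wide wording may be habit. This stands in part: the misgrading is a possible result of the text, not a certain one. It does not remove the mismatch, because the laboratory section goes on to state the limit and the AE section does not.

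The reach is also narrow. It needs the same preferred term, recorded as an AE in two phases, at different grades. An ALT flare, the obvious example, may not qualify, since protocol 9.7 states that "Laboratory abnormalities are usually not recorded as AEs or SAEs". The exceptions include abnormalities needing medical intervention. A flare that leads to NrtI restart could reasonably be read as one, but that is inference. After the February 2023 announcement, the Treatment Stopping Criteria no longer applied to subjects who then reached Week 48 (SAP 1.2), which limits off-treatment data. The SAP still orders the off-treatment and restart tables. Finally, "A data listing containing all AEs will be provided", so any shifted grade can be traced.

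A reader might infer three stronger things that the documents do not support:

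- *The rule moves severity onto the study drugs, mainly in the arms where more subjects stop all therapy.* It repeats the worst grade in either direction, and no stopping rates by arm are given.
- *One or two shifted events would change the safety picture, because only 2 of 92 subjects (2%) in Study 211 had a Grade 3 or 4 TEAE.* That figure counts subjects with any such event over 24 weeks of VBR+NrtI. The table here is by preferred term, over a planned 48 weeks of treatment, and includes AB-729 arms.
- *The primary endpoint is distorted.* The endpoint is the proportion with AEs, with discontinuation due to AEs and with abnormal laboratory results. AE grade is not part of it.

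**Conclusion.** The point holds as a scope error in one rule. As written, the severity rule in SAP 7.1.6 covers the whole study while its tables cover single phases, and applying it literally can place a grade from one phase in another phase's table. The consequence is confined to the TEAEs-by-severity-grade table and to subjects with the same preferred term at different grades in more than one phase.

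The size per subject, 3.3 or 6.7 percentage points, assumes the planned group sizes as denominators. SAP 7.1.6 does not state the denominator for the phase tables, and a smaller one would make each share larger. The documents do not give the number of such subjects, and it may be zero. This is a minor correction, worth making because it removes a second reading from a required safety summary.

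**What to change.** In SAP 7.1.6, end the severity rule with *during the phase being summarized* in place of *during the study*, which matches the limit in SAP 7.2.1.2. Add one sentence saying that each AE is assigned to a phase by its onset date, using the boundaries in SAP 3.6.3.

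If version 2.0 of the SAP is already final, record both points in the Synoptic CSR, where SAP section 1 says that later changes will be documented. The cost is a few words and, at most, a check that the severity table was programmed with the within-phase maximum. No new data are needed.

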## **7.2. Laboratory Evaluations**

### **7.2.1. Graded Laboratory Values**

The criteria specified in the study protocol will be used to grade laboratory results as normal (no grade), mild (Grade 1), moderate (Grade 2), severe (Grade 3) or potentially life threatening (Grade 4). See Appendix 1 of the protocol for detailed DAIDS grading criteria on the relevant laboratory tests. For laboratory tests with criteria for both increased and decreased levels, analyses for each direction (ie, increased, decreased) will be presented separately.

#### **7.2.1.1. Treatment-Emergent Laboratory Abnormalities**

Treatment-emergent laboratory abnormalities are defined as values that increase at least 1 toxicity grade from Baseline at any postbaseline time point. If the relevant baseline laboratory value is missing, any abnormality of at least Grade 1 observed within the time frame specified above will be considered treatment emergent.

#### **7.2.1.2. Summaries of Laboratory Abnormalities**

A summary (number and percentage of subjects) for treatment-emergent laboratory abnormalities will be provided by lab test and treatment group; subjects will be categorized according to the most severe postbaseline abnormality grade for a given laboratory test.

Treatment-emergent lab abnormalities will be summarized based on the Safety Analysis Set. Tables will be created per study phase (i.e. On-Treatment Phase, Off-Treatment Phase, and NrtI-Restart Phase).

For all summaries of laboratory abnormalities, the denominator is the number of subjects with nonmissing postbaseline values in each phase.

The maximum post-baseline grade in each phase will be tabulated for each laboratory test, and percentages will be based on the number of subjects with a post-baseline evaluation of the specific laboratory test. The laboratory abnormalities during the follow-up period will also be summarized.

A by-subject listing of graded laboratory abnormalities will be provided by subject ID number and visit in chronological order. This listing will include all test results that were collected throughout the study for the lab test of interest, with all applicable severity grades displayed.

### **7.2.2. Ungraded Laboratory Values**

Treatment-emergent abnormal direct bilirubin will be summarized by cohort and treatment group. A treatment-emergent abnormal direct bilirubin record is defined as a record with value > baseline and  $\geq$ ULN in the phase. The highest direct bilirubin measurement will be counted for each subject. A by-subject listing of visits

Treatment-emergent abnormal direct bilirubin will be summarized based on the Safety Analysis Set. Tables will be created per study phase (i.e. On-Treatment Phase, Off-Treatment Phase, and NrtI-Restart Phase).

### **7.2.3. ALT Elevation**

#### **7.2.3.1. ALT Elevation without Declining Hepatic Function**

All subjects with an ALT elevation on treatment, defined as  $ALT > 2 \times$  Baseline or on-treatment nadir and  $\geq 10 \times$  ULN, should have the ALT findings confirmed within 3 days of receipt of the original results.

#### **7.2.3.2. ALT Elevation with Declining Hepatic Function**

Subjects with confirmed ALT elevation with evidence of declining hepatic function should be discontinued prematurely from study treatment. This is defined as:

- ALT elevation  $\geq 2 \times$  Baseline (Day 1) or nadir and  $> 2 \times$  ULN AND
- Direct bilirubin increase to  $\geq 2 \times$  Baseline (Day 1) and  $\geq 2 \times$  ULN OR
- Albumin decline  $\geq 0.5$  g/dL from Baseline OR international normalized ratio (INR)  $> 2 \times$  Baseline (Day 1) OR
- Symptoms of liver inflammation (eg, fatigue, weakness, lack of appetite, nausea, vomiting, jaundice or discolored feces)

The number of subjects meeting the above criteria will be summarized by treatment group. Clinical signs or symptoms of liver inflammation will not be included in the summary. For individual laboratory tests, subjects will be counted once based on the most severe postbaseline values. For the composite criteria, subjects will be counted once when the criteria are met at the same visit. The denominator is the number of subjects in the Safety Analysis Set who have nonmissing postbaseline values. A listing of subjects who met at least 1 of the above criteria will be provided.

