    - If ALT is rising at the confirmatory visit, subjects should return for an Unscheduled Visit every 2 to 5 days until the ALT elevation has stabilized. At these visits, the following laboratory tests will be performed: ALT, AST, total bilirubin (if total bilirubin is elevated, reflex to direct bilirubin), serum albumin, INR, creatine kinase, HBV DNA, quantitative HBV serologies (HBeAg [reflex qualitative HBeAg if quantitative HBeAg is negative] and HBsAg [reflex qualitative HBsAg if quantitative HBsAg is negative]). The Investigator will determine if other assessments specified in [Section 8.4](#) should be performed. Subjects whose ALT has stabilized should continue to be monitored weekly (or more frequently, as deemed necessary by the Investigator) until ALT values return to normal or Baseline levels.
    - Subjects with an ALT elevation without declining hepatic function and without contraindications should discontinue study drug if the ALT remains persistently elevated for  $>4$  weeks
- ALT Elevation With Declining Hepatic Function

[figure not shown]
- Subjects with confirmed ALT elevation with biochemical evidence of declining hepatic function should be discontinued from study treatment. This is defined as:
  - ALT elevation  $\geq 2 \times$  Baseline or nadir and  $> 2 \times$  ULN AND
    - Direct bilirubin increase to  $\geq 2 \times$  Baseline and  $\geq 2 \times$  ULN OR
    - Albumin decline  $\geq 0.5$  g/dL OR INR  $> 1.5 \times$  Baseline OR
    - Symptoms of liver inflammation (eg, fatigue, weakness, lack of appetite, nausea, vomiting, jaundice, or discolored feces)
- Subjects with evidence of declining hepatic function should return for an Unscheduled Visit every 2 to 5 days until the relevant laboratory values stabilize. Subjects whose hepatic function has stabilized should continue to be monitored weekly (or more frequently as deemed necessary by the Investigator) until the relevant laboratory values return to normal or Baseline.

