Section 9.10.4	
The following changes have been made:
 
Paragraph 2:
 
 
○ All subjects with an ALT elevation on treatment, defined as ALT >2× Baseline or on treatment nadir and ≥10× ULN, should have the ALT findings confirmed within 3 days of receipt of the original results. All subjects should return for an Unscheduled Visit. <del>At this visit subjects will undergo a symptom directed physical examination, vital signs, review of concomitant medications and AEs, and the following laboratory tests: ALT, AST, total bilirubin (if total bilirubin is elevated, reflex to direct bilirubin), serum albumin, creatine kinase and INR. The Investigator will determine if other assessments specified in Section should be performed.</del>
 
 
Paragraph 3:
 
 
○ If the ALT elevation is confirmed, then an additional Unscheduled Visit will be performed to further evaluate the subject. At this visit, the following laboratory tests will be performed: ALT, AST, total bilirubin (if total bilirubin is elevated, reflex to direct bilirubin), serum albumin, INR, creatine kinase, HBV DNA, quantitative HBV serologies (HBeAg [reflex qualitative HBeAg if quantitative HBeAg is negative] and HBsAg [reflex qualitative HBsAg if quantitative HBsAg is
 
	
The edits clarify the sequence of assessments and laboratory tests to be followed in the event of ALT elevation in subjects.
 
The tests for ANA, smooth muscle antibodies and anti-LKM1 antibodies, EBV DNA, CMV DNA, HSV DNA, and total IgG, have been added to exclude other etiologies for ALT elevation.
 
Albumin decline INR >1.5 is more conservative than >2 and is supported by scientific literature.
 
The reference to the US FDA has been deleted since Study 204 is not being conducted in the USA.
 
The figure has been added for clarity.

Section (In Original Protocol)	Change Made	Rationale

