## 1. INTRODUCTION

Study ABI-H0731-204 is a randomized Phase 2a, multicenter, open-label, multiple-cohort study evaluating the safety and antiviral activity of Vebicorvir (VBR) and AB-729 in combination with other chronic hepatitis B virus (HBV) infection (cHBV) treatments in subjects with cHBV. The target population is male or female subjects, 18 to 50 years of age, inclusive, with no evidence of cirrhosis or end-stage liver disease. Cohort 1 is prespecified and will enroll virologically-suppressed subjects on nucleos(t)ide reverse transcriptase inhibitor (NrtI) therapy with hepatitis B virus “e” antigen (HBeAg) negative cHBV. Approximately 60 subjects will be enrolled in Cohort 1 of this study. Up to 2 additional cohorts, with approximately 60 subjects per cohort, may be added in future protocol amendments, for a maximum sample size of approximately 180 subjects.

This statistical analysis plan (SAP) describes the statistical analysis methods and data presentations to be used in tables, figures, and listings (TFLs) in the clinical study report (CSR) for Study ABI-H0731-204. This SAP is based on the study protocol Amendment 1, dated 27 October 2021 and the electronic case report form (eCRF). In February 2023, Assembly and Arbutus jointly made the decision to discontinue study ABI-H0731-204, following the observation that AB-729 in dual combination with NrtI alone and as a triple combination with VBR promoted similar on-treatment declines in HBsAg, as has been observed in other AB-729 studies. Thus, there appears to be limited additional benefit to subjects continuing in the post-treatment study period as currently defined in the protocol. The study was prematurely terminated after every active subject completed 48-week treatment period.

The SAP will be finalized before database lock. Only key safety and efficacy endpoints will be performed. Any changes made after the finalization of the SAP will be documented in the Synoptic CSR.

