**Table 1-2. Subject Treatment Assignment for Study ABI-H0731-204 Cohort 1**

Treatment Group	Study Treatment	Mode of Delivery	Number of Subjects per Group
1	VBR+AB-729+NrtI	VBR and NrtI: Oral; AB-729: Subcutaneous	30
2	VBR+NrtI	Oral	15
3	AB-729+NrtI	AB-729: Subcutaneous;	15

---

---

NrtI: Oral	
Total Subjects Planned:	60

---

Abbreviations: NrtI=nucleos(t)ide/reverse transcriptase inhibitor; VBR=vebicorvir.

This is a proof-of-concept study. The sample size is similar to that previously utilized for this type of study and is not based upon statistical considerations.

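### SAP 7.2.3.2 counts INR only above 2 times Baseline, but the protocol version it follows sets the limit at 1.5 times Baseline

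*Combined protocol and SAP*

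**What the plan says.** SAP Section 7.2.3.2 restates the criteria for ALT elevation with declining hepatic function and gives the INR limit as "international normalized ratio (INR) $> 2 \times$ Baseline (Day 1"). It then plans counts by treatment group at two levels.

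- **Single tests:** "For individual laboratory tests, subjects will be counted once based on the most severe postbaseline values".
- **Composite:** a subject counts once if the criteria are met at the same visit. Symptoms are left out of this summary.

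It also plans a listing: "A listing of subjects who met at least 1 of the above criteria will be provided".

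Protocol Section 9.10.4, in its current text, gives the INR limit for the same composite as "INR $> 1.5 \times$ Baseline OR" (the closing word links it to the next criterion). The SAP Introduction names its source: "This SAP is based on the study protocol Amendment 1, dated 27 October 2021".

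**The concern.** The two documents define one safety event with two different INR limits. The SAP limit is the laxer one, and it equals the value that Amendment 1 replaced. The amendment's stated reason, in protocol Appendix 3, is that an INR limit of "1.5 is more conservative than" a limit of 2. The protocol value was therefore a considered choice. The SAP's document history records only a compliance update for version 2.0, and nothing in Section 7.2.3.2 explains a departure. A carry-over of the older value is the likeliest explanation.

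Safety and tolerability are the primary objective, and abnormal laboratory results are part of the primary endpoint. A report built on the SAP could show fewer laboratory-defined cases of hepatic decline than the protocol's own limits would give.

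**Working it through.** No formula produces the threshold, so the check is a comparison of the two current texts followed by simple arithmetic on the gap.

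**1. Component by component**

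| Component | Protocol 9.10.4 (Amendment 1) | SAP 7.2.3.2 | Same? |
|---|---|---|---|
| ALT | ≥2 × Baseline or nadir, and >2 × ULN | ≥2 × Baseline (Day 1) or nadir, and >2 × ULN | Yes |
| Direct bilirubin | ≥2 × Baseline and ≥2 × ULN | ≥2 × Baseline (Day 1) and ≥2 × ULN | Yes |
| Albumin | Fall of ≥0.5 g/dL | Fall of ≥0.5 g/dL, measured from Baseline | Yes in substance |
| INR | >1.5 × Baseline | >2 × Baseline (Day 1) | **No** |
| Symptoms | Qualify a subject | Listed, but excluded from the summary | Stated difference |

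INR is the only laboratory component whose limit differs. The comparison is between the protocol body and the SAP body. The amendment log serves only to show where the value 2 came from. Protocol Figure 7 is not reproduced in the available text and could not be checked.

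**2. Who is missed**

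The composite is ALT AND (direct bilirubin OR albumin OR INR). A subject counted under the protocol's laboratory limits but not under the SAP's must, at one visit:

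- meet the ALT criterion;
- have 1.5 × Baseline < INR ≤ 2.0 × Baseline;
- be negative on direct bilirubin and on albumin.

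The single-test INR row needs less. It misses any subject whose most severe postbaseline INR falls in that band.

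**3. Width of the band**

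The documents give no Baseline INR values, so those below are assumed.

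| Assumed Baseline INR | Protocol limit (1.5 × Baseline) | SAP limit (2 × Baseline) | Band not counted |
|---|---|---|---|
| 0.9 | 1.35 | 1.80 | >1.35 to 1.80 |
| 1.0 | 1.50 | 2.00 | >1.50 to 2.00 |
| 1.2 | 1.80 | 2.40 | >1.80 to 2.40 |

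**4. Weight of one omitted subject**

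SAP Table 1-2, column "Number of Subjects per Group", plans 30, 15 and 15.

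- Group 1: 1/30 = 3.3 percentage points.
- Group 2 or 3: 1/15 = 6.7 percentage points.

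The SAP's denominator is Safety Analysis Set subjects with nonmissing postbaseline values. A smaller denominator would make each omitted subject weigh slightly more.

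**The case against.** The mismatch itself is not in dispute. The case against giving it weight has four parts.

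- **The consequence is small.** The table is descriptive, in a Synoptic CSR for a terminated study. Subjects are discontinued under the protocol, and its rule for notifying agencies at 5 or more subjects also runs under the protocol. The omitted subject must fit a narrow profile, and none is known to exist. All of this stands, and it caps the severity.
- **The data appear elsewhere.** INR is graded in protocol Appendix 1 from 1.1 × ULN, and SAP Section 7.2.1.2 tabulates graded abnormalities by test and treatment group. If ULN is assumed to be 1.1 to 1.2, an INR of 1.35 is 1.35/1.2 = 1.13 to 1.35/1.1 = 1.23 × ULN, which is Grade 1. So the rise would probably be visible. However, grading is against ULN and one test at a time, so it cannot replace a Baseline-relative criterion assessed together with ALT at the same visit.
- **The listing covers the gap.** The omitted subject should appear in it through ALT. That helps, but the listing is a screen. Under a limit of 2 it would not mark that subject as meeting the INR criterion or the composite.
- **The fix does not restore the full protocol count.** This is correct, because the SAP leaves symptoms out. That exclusion is stated openly, whereas the INR change is not. Correcting INR brings the laboratory part into line and leaves the symptom difference as disclosed.

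**Conclusion.** The concern holds: the SAP's INR limit is wrong as written. It contradicts the current text of the protocol version on which the SAP says it is based, reverts to a replaced value, and gives no reason. Two planned counts are affected, the INR row and the laboratory composite, and both can only be too low against the protocol's limits.

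The size is conditional: 3.3 percentage points per omitted subject in Group 1 and 6.7 in Group 2 or 3, at planned numbers. These figures show the weight of one subject. They do not estimate how many subjects are affected. Treatment decisions are untouched. This should be fixed because it concerns a safety summary and the correction is cheap, but it does not threaten the trial's conclusions on present evidence.

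**What to change.** In SAP Section 7.2.3.2, set the INR limit to more than 1.5 times Baseline (Day 1). Use it in both the single-test INR row and the composite, and program the composite as ALT AND (direct bilirubin OR albumin OR INR). Keep the existing note that symptoms are not counted, so that the table reads as a laboratory-only version of the protocol definition. A further row at more than 2 times Baseline is optional. If the sponsor did intend 2, the SAP should say so and why.

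If the SAP is already final, apply the corrected limit and use the route the SAP provides: "Any changes made after the finalization of the SAP will be documented in the Synoptic CSR".

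The cost is one constant in one derivation and one line of documentation. INR is already collected in the coagulation panel at every scheduled visit from Day 1 on, so no new data are needed.
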